5.3.3.8 Hepatitis Flares

The number and proportion of patients having any episode of hepatitis flares across all study visits during the treatment period will be analyzed by treatment arm and overall.

The following analyses will also be reported by treatment arm and overall:

- Incidence of hepatitis flares per patient;
- Maximum and average of duration of hepatitis flares by patient. This will be analyzed by means
 of descriptive statistics including mean, standard deviation, median, Q1 and Q3, minimum and
 maximum.

A listing for hepatitis flares will be created.

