3.4. Safety Endpoints

- Incidence and severity of AEs, medically-attended AEs (MAEs), new-onset chronic illnesses (NCIs), and immune-mediated medical conditions (IMCs)
- Incidence and severity of local and systemic reactogenicity events
- Incidence and duration of hepatitis flares, defined as alanine aminotransferase (ALT) \geq 3 × upper limit of normal (ULN) and \geq 100 U/L
- Changes in ALT, aspartate aminotransferase (AST), alkaline phosphatase (AP), gamma glutamyl transferase (GGT), bilirubin total and direct, international normalized ratio (INR) and other laboratory parameters

Safety endpoints will be assessed separately for the 24-week Treatment Period and 52-week Follow-Up Period.

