- 1 If an authorized COVID-19 vaccine has been administered in proximity to a scheduled IP administration, a ± 3 day window is allowed for IP dosing.
- ^m After Day 169 or ET, only MAEs, NCIs and IMCs will be recorded.
- ⁿ A single blood sample will be collected for biobanking at the beginning of the study (prior to dosing on Day 1) and end of the study. This sample will be used for future analyses not specified in the protocol. Analysis will be limited to HBV serologic and HBV-specific DNA and RNA and patients' DNA will not be analyzed.
- ° Safety laboratory testing, including liver panel, for Doses 1 and 2 will be obtained during the visits conducted 7±2 days after these doses of study medication. Safety laboratory testing following Doses 3, 4 and 5 will be obtained in the interval from 7 days after dose administration and before the next dose of study medication is administered. Safety labs after Dose 6 will be assessed at the Day 169 visit.
- ^p Diaries will also be reviewed at the Day 85, Day 113, Day 141 and Day 169 visits

Table 2 Schedule of Events – Follow-up Period

	Follow-Up Period					
Study Visit	Day 232	Day 323	Day 414	Day 505 or ET ^a		
Completion of Week (number)	33	46	59	72		
Window (days)	±10 days	±10 days	±10 days	±10 days		
Visit may be conducted at home or work or in part as a telemedicine visit ^b	X		X			
Immunosuppressive medications, vaccines, and new HBV treatments (only) ^c	X	X	X	X		
Targeted and symptom-driven PE	X	X	X	X		
Height and weight				X		
Vital signs ^d	X	X	X	X		
ECG ^d				X		
Hematology and serum chemistry	X	X	X	X		
Liver panel	X	X	X	X		
HBV serology and viral markers ^e		X		X		
Whole blood for PBMC isolation		X		X		
MAEs, NCIs and IMCs (only) ^f	X	X	X	X		

AE = adverse event; ECG = electrocardiogram; ET = early termination; HBV = hepatitis B virus; HIV = human immunodeficiency virus; MAE = medically-attended adverse event; NCI = new-onset chronic illness; IMC = immune-mediated medical condition; PBMC = peripheral blood nonnuclear cell; PE = physical examination.

^a If a patient prematurely discontinues study medication before Day 505, Day 505/Early termination procedures will be performed.

^b A telemedicine visit would include a home visit by appropriate trained personnel to perform a target and symptom-driven physical and obtain vital signs and safety laboratories. The remaining portions of the visit may be conducted virtually by the study investigator.

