8.3.3. Clinical Laboratory Tests

Blood samples for the safety laboratory tests listed in Table 3 will be collected according to the Schedule of Events (Section 4.6).

Table 3: Safety Laboratory Tests

Hematology

White blood cells (WBC) Platelets

Red blood cells WBC differential (absolute and %)

HemoglobinNeutrophilsHematocritLymphocytesMean corpuscular volumeMonocytesMean corpuscular hemoglobinEosinophilsMean corpuscular hemoglobin concentrationBasophils

Liver Panel

Total and direct bilirubin

Aspartate transaminase (AST)

Alanine aminotransferase (ALT)

Total protein

Albumin

Gamma-glutamyl transferase (GGT)

Lactate dehydrogenase

Alkaline phosphatase (AP)^a

International normalized ratio (INR)

Serum Chemistry

Sodium

Potassium

Urea

Creatinine

Calcium

Phosphate

Glucose

Creatine kinase^b

Urinalysis

Protein Red blood cells

Bilirubin pH Urobilinogen Nitrites

Ketones Specific gravity

Glucose Microscopy (if clinically indicated or Leukocyte esterase hemoglobin is detected on dipstick)

For the purpose of reactogenicity reporting, hematuria is defined as 3 or more red blood

cells per high powered field

Serology (at Screening only)					
HIV I and II	HDV antibodies				
HCV antibodies					
Drugs of abuse and alcohol screen (at Screening only) ^c					
Amphetamine/ecstasy	Opiates				
Ethanol	Benzodiazepines				
Cannabinoids	Methadone and/or metabolites				
Cocaine	Barbiturates				
Pregnancy test ^d					

Pregnancy test

Beta human chorionic gonadotropin

- a Alkaline phosphatase iso-enzymes (liver-specific and bile duct specific) will be measured if original alkaline phosphatase test result is above the upper limit of normal.
- b Creatine kinase MB or Troponin T will be measured where clinically indicated.
- c Sites may use locally available drugs of abuse panels and alcohol tests. The specific drugs may vary from the outlined list.
- d A serum pregnancy test will be performed in all women of childbearing potential at Screening. Urine pregnancy tests will be performed at other time points.

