4.3 Safety Endpoints

- Incidence and severity of AEs, medically-attended AEs (MAEs), new-onset chronic illnesses (NCIs), and immune-mediated medical conditions (IMCs)
 - An MAE is an AE resulting in hospitalization, emergency room visit, or visit to or from medical personnel (other than routine health care visits).
 - An NCI is an AE that is new (i.e., not present at baseline) and typically chronic. Because of the significance of this designation for the patient's health and for evaluation of vaccine safety, NCIs are expected to be diagnoses, not symptoms, and the Investigator should record sufficient data in the source document to support the diagnosis.
 - An IMCs is any AE appearing in the list of AEs detailed in Appendix 2 of the protocol. Any AE
 assessed by the Investigator as immune-mediated but not appearing in the list will also be
 reported as an IMC.
- Incidence and severity of local and systemic reactogenicity events
 Reactogenicity local or systemic events, and oral temperature will be recorded by the patient in a diary daily for 7 days after each dose. Events will be graded according to the FDA Guidance for

Industry: Toxicity Grading Scale for Healthy Adult and Adolescent Volunteers Enrolled in Preventive Vaccine Clinical Trials [United States Food and Drug Administration 2007].

Reactogenicity events will be categorized separately from AEs unless they are assessed as serious, in which case they will be reported as SAEs. The solicited reactogenicity events are the following:

Local (injection site) reactogenicity events:

- Pain at injection site (without pressure)
- Redness
- Swelling or hardening
- Tenderness

Systemic reactogenicity events

- Fatigue
- Fever
- Chills
- Headache
- Muscle aches
- Joint aches
- Nausea
- Vomiting
- Diarrhoea

Unsolicited events reported by the patients outside of this 7-day reporting period will be recorded as AEs.

Incidence and duration of hepatitis flares;

Hepatitis flares are defined as alanine aminotransferase (ALT) \geq 3 × upper limit of normal (ULN) and > 100 U/L.

The incidence and duration of hepatitis flares will be estimated considering ALT values across all measurements taken (scheduled and repeated) during the treatment period, as follows:

- Incidence of hepatitis flares will be estimated with the number of episodes across measurements on the treatment period per patient.

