Safety endpoints that are also measured during the Follow-Up period will be assessed separately for the 24-week Treatment Period and 52-week Follow-Up Period.

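### The SAP limits hepatitis flares to the treatment period, against Protocol 3.4 and its own two-period rule, so follow-up ALT has no flare summary by arm

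*SAP*

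**What the plan says.** Protocol 3.4 lists the incidence and duration of hepatitis flares, defined from ALT, among the safety endpoints. It closes with a rule for the whole list: "Safety endpoints will be assessed separately for the 24-week Treatment Period and 52-week Follow-Up Period".

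SAP 4.3 carries the rule over with one condition: "Safety endpoints that are also measured during the Follow-Up period will be assessed separately for the 24-week Treatment Period and 52-week Follow-Up Period".

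The same SAP section, where it defines the flare variables, says they are estimated "considering ALT values across all measurements taken (scheduled and repeated) during the treatment period". SAP 5.3.3.8 then sets the analysis: "The number and proportion of patients having any episode of hepatitis flares across all study visits during the treatment period will be analyzed".

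Other relevant provisions:

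- **ALT in follow-up.** Protocol Table 2 schedules a liver panel at all four follow-up visits, and Protocol Table 3 includes ALT in that panel. SAP 5.3.3.12 says the panel is evaluated on the scheduled follow-up days.
- **Comparable endpoints.** SAP 5.3.3.4 to 5.3.3.6 give medically-attended adverse events (MAEs), new-onset chronic illnesses (NCIs) and immune-mediated conditions (IMCs) a separate assessment in each period.
- **Declared changes.** SAP 5.3.17 lists one departure from the protocol's analyses, which concerns ECG parameters.
- **Outputs.** SAP Appendix 1 marks the biochemistry tables as running through Day 169. The addendum written after termination adds follow-up tables for MAEs, NCIs and IMCs, and otherwise listings.

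**The concern.** A named safety endpoint is analysed for one of its two required periods, and no reason is given. The protocol treats flares after Day 169 as something that may happen: Protocol 4.1 keeps recording medications associated with hepatitis flares or hepatic injury beyond that day, although most other medication recording stops.

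What is at stake is how the safety report can be read. If the tables are produced as specified, the flare table covers the treatment period only, and the absence of follow-up flares from the tables would say nothing about whether any occurred. After Day 169 only MAEs, NCIs and IMCs are recorded as adverse events (Protocol 8.3.2). An ALT rise that meets the flare definition but is not recorded under one of those headings has no place in any follow-up summary by arm. A flare still present at Day 169 would also have its duration cut there.

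**Working it through.** The documents give no figure to reproduce. The check is a comparison of text plus day arithmetic on the planned schedule.

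**1. Does the SAP's two-period rule apply to flares?** Its condition is that the endpoint is also measured in follow-up. Flares are derived from ALT, and ALT is in the liver panel scheduled at Days 232, 323, 414 and 505. The condition is met.

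**2. Do the flare sections follow the rule?**

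| Place | Period for flares |
|---|---|
| Protocol 3.4 | Both, separately |
| SAP 4.3, closing rule | Both, separately |
| SAP 4.3, flare derivation | Treatment period only |
| SAP 5.3.3.8 | Treatment period only |
| SAP 5.3.17 | No change declared |

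They do not, and the conflict lies within the SAP as well as between the SAP and the protocol.

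**3. How much scheduled ALT is left out?** Inputs are the visit days in Protocol Tables 1 and 2 and the last dose at Day 141.

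- Follow-up visits at 13, 26, 39 and 52 weeks after the last dose: 141 + 7×13 = 232; 141 + 7×26 = 323; 141 + 7×39 = 414; 141 + 7×52 = 505. These match Table 2.
- Post-baseline ALT visits in the treatment period: Days 8, 29, 36, 57, 85, 113, 141 and 169, which is 8. In follow-up there are 4. Left out: 4/(8 + 4) = 4/12, one third.
- Time left out: 505 − 169 = 336 days, and 336/7 = 48 weeks. Total after Day 1: 504 days, and 504/7 = 72 weeks. Share: 336/504 = 66.7%.
- The 52-week follow-up runs from the last dose, so its first 28 days (169 − 141) fall in the treatment period and are covered. Share of time after the last dose left out: 336/(505 − 141) = 336/364 = 92%.

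**4. Does another follow-up table by arm pick up the missing flares?**

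- MAE, NCI and IMC follow-up tables: only if the event was recorded as one of these.
- Biochemistry summaries, abnormality counts and shift tables: SAP 5.3.3.12 describes them for follow-up visits, but Appendix 1 stops them at Day 169 and the addendum does not extend them.
- Listings of biochemistry (16.2.8.2) and of hepatitis flares (16.2.10.1): produced for all patients in the database, but they are not summaries. Under the SAP 4.3 derivation the flare listing would hold treatment-period episodes only.

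**5. What can follow-up ALT support?** Scheduled visits are 91 days apart (323 − 232). SAP 4.3 computes duration as stop date minus start date plus 1, so a flare seen at one scheduled visit and gone at the next gets 91 + 1 = 92 days. With the ±10-day windows the range is 71 + 1 = 72 to 111 + 1 = 112 days, whatever the true length. Incidence can be counted; duration is coarse.

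**The case against.** Several points on the other side have force.

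- **The SAP takes precedence.** Protocol 10.6 lets the SAP supersede the protocol except for the primary analysis, so a departure from Protocol 3.4 could be legitimate. This stands as far as it goes. It does not settle a conflict between two statements in the SAP, and 5.3.17 does not declare the change.
- **Termination.** The study was stopped after the Week 24 analysis, so follow-up is incomplete. This limits the size of the problem but does not explain the omission: SAP section 2 still promises accrued safety information in tables and listings up to termination, and three other safety endpoints keep follow-up tables.
- **Other routes exist.** A reader might infer that a flare without medical attendance reaches no follow-up table. That is too strong. A clinically significant laboratory abnormality is an adverse event (Protocol 9.4), and any adverse event the investigator judges immune-mediated is reported as an IMC (Protocol Appendix 2), which has a follow-up table. The gap is a flare recorded under none of the three headings.
- **Listings.** SAP 5.3 says listings are generally sorted by arm, and with about 80 patients ALT elevations could be counted by hand from the biochemistry listing. This is true, so the data are not lost. It is still no substitute for a planned summary of a named endpoint.
- **Ambiguous index.** Appendix 1 marks the flare incidence table (14.3.6.1) as included without the Day 169 limit that it puts on laboratory tables. This suggests unreconciled wording rather than a decision to exclude follow-up. It does not override the explicit text of 4.3 and 5.3.3.8, and the addendum does not regenerate the table.

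**Conclusion.** The point holds. The SAP restricts flare derivation and analysis to the treatment period although its own rule and Protocol 3.4 require both periods, ALT is measured in both, and no change is declared. On the planned schedule this omits 4 of 12 post-baseline ALT visits and 48 of 72 weeks. Those figures assume complete follow-up to Day 505; the amount actually accrued before termination is smaller and not stated.

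Two stronger readings are not supported. A reader might infer that flares after dosing go uncounted, but those occurring between doses and up to Day 169, 28 days after the scheduled last dose, are within the analysis; the gap begins after Day 169. A reader might also infer that delayed flares are a main liver-safety concern for this product. The documents do not say so: Protocol 1.3 reports no flares in Phase 1, and Protocol 4.3 discusses flares as something that could preclude the next scheduled dose. The case rests on the endpoint being named and half analysed.

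This should be corrected before the final report. It does not affect the efficacy conclusions.

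**What to change.** - In SAP 4.3 (flare derivation) and 5.3.3.8, remove the restriction to the treatment period and apply the existing flare definition to all ALT values accrued up to termination.
- Add a follow-up table of flare incidence by arm, with person-time at risk, since termination truncated follow-up unequally across patients enrolled at different times. State how an episode spanning Day 169 is assigned, for example to the period in which it started.
- Report follow-up duration descriptively only, noting the 91-day visit spacing.
- Include follow-up episodes in Listing 16.2.10.1 and add the new table to Appendix 1 and the addendum.
- If the restriction is intended, declare it with its reason in 5.3.17 and amend the closing rule of SAP 4.3.
- Minor: the ALT threshold is above 100 U/L in the SAP and at or above 100 U/L in the protocol. Reconcile the two; only a value of exactly 100 U/L is affected.

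The cost is one additional table and a few lines of text. No new data are needed.

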5.3.3.9 Physical Exam

Physical examination after baseline maybe targeted and symptom-driven for all study visits and only at the end of the Treatment Period (Day 169 or ET) a complete examination will be performed.

Results of physical examination assessments will be summarized by treatment arm and overall for each visit and by system class (in case of complete examination), as follows:

- Normal

- Abnormal Not Clinically Significant
- Abnormal Clinically Significant

Targeted and symptom-driven physical examination data during the treatment period will be summarized in the current visits: Day 1, 8, 29, 36, 57, 85, 113, and 141. Visits Day 64, Day 92, Day 120 and Day 148 for collection of this data during the treatment period were removed in the protocol version for which this SAP version is planned.

For patients following previous versions of the protocol, data recorded on the legacy visits will be used for analyses if an additional abnormality was reported. Data will be used for analyses following the correspondence: Day 64 to Day 85; Day 92 to Day 113; Day 120 to Day 141.

Post-baseline physical exams and the significant findings will be listed on a by-patient basis.

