5.3.3.11 Vital Signs and Height, weight, and BMI

A summary of vital signs (including systolic and diastolic blood pressure and body temperature (in °C), heart rate and respiratory rate) including change from baseline (where appropriate), presented by descriptive statistics, will be displayed by treatment arm and overall, for each visit day from baseline through Day 169. Particularly, for vital signs measured after first and second doses, the maximum value among all values recorded in the 2 hours post-dosing will be taken as the representative for that day in summaries by visit.

Vital Signs data during the treatment period will be summarized in the current visits: Day 1, 8, 29, 36, 57, 85, 113, 141 and 169. Visits Day 64, Day 92, Day 120 and Day 148 for collection of Vital Signs data during the treatment period were removed in the protocol version for which this SAP version is planned.

For patients following previous versions of the protocol, data recorded on the days of the current visits listed above will be used for analyses. Only if there is no data collected in these visits and these patients have additional values in visits previously collected, those data will be used for analyses following the correspondence: Day 64 to Day 85; Day 92 to Day 113; Day 120 to Day 141; Day 148 to Day 169.

In addition, a summary and change from pre-dose of the values measured in the 2 hours post-dose (at 15 minutes intervals) after the first and second doses will be presented using the maximum value among

all values recorded in the 2 hours post-dosing. Pre-dose will be the latest assessment prior to the dose being summarized.

Height, weight, and BMI and the corresponding change from baseline will be summarized for visits after baseline.

Only available data will be used, and missing data will not be imputed. Change from baseline and predose will be calculated only for patients with non-missing values for both the baseline or pre-dose and the time-point of interest and will be missing otherwise.

Vital Signs (on dosing and no-dosing days) and height, weight and BMI after baseline will be listed.

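### Physical examinations from removed visits enter the Day 85, 113 and 141 rows only when abnormal, so those rows can only be raised and are not comparable with Days 1 to 57

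*SAP*

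**What the plan says.** SAP 5.3.3.9 records that "Visits Day 64, Day 92, Day 120 and Day 148 for collection of this data during the treatment period were removed in the protocol version". Targeted examinations "will be summarized in the current visits: Day 1, 8, 29, 36, 57, 85, 113, and 141". For patients on earlier protocol versions, "data recorded on the legacy visits will be used for analyses if an additional abnormality was reported", and the mapping is "Day 64 to Day 85; Day 92 to Day 113; Day 120 to Day 141". Day 148 has no entry. Day 169 is not in the targeted list because "only at the end of the Treatment Period (Day 169 or ET) a complete examination will be performed"; Appendix 1 gives it its own table (14.3.9.1.1), with targeted examinations in Table 14.3.9.1.2.

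SAP 5.3.3.11 treats vital signs from the same removed visits differently. The current visit's reading is used. Only when that visit has no data does a legacy reading stand in: "those data will be used for analyses following the correspondence: Day 64 to Day 85; Day 92 to Day 113", continuing with Day 120 to Day 141 and Day 148 to Day 169.

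**The concern.** Whether a legacy examination is used depends on what it found. For an earlier-version patient, the Day 85 row reflects the Day 85 examination plus any additional abnormality from Day 64. For a current-version patient it reflects the Day 85 examination alone. The same holds at Days 113 and 141.

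Two things follow. The three rows overstate how often the examination due at that visit is abnormal. They also stop being comparable with Days 1, 8, 29, 36 and 57, where no merging takes place. A reader scanning the table by dose could see abnormalities rise from Dose 3 onward when part of the rise comes from the rule. Separately, an abnormal targeted examination on Day 148 has no stated row.

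**Working it through.** The plan states no figure for this point, so the check sets the rules side by side and then illustrates the direction.

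**Timing.** Doses fall on Days 1, 29, 57, 85, 113 and 141 (SAP 2.3.3).

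| Legacy day | Time after dose | Examination row | Vital-sign row | Gap to vital-sign row |
|---|---|---|---|---|
| 64 | 64 − 57 = 7 days after Dose 3 | 85 | 85 | 21 days |
| 92 | 92 − 85 = 7 days after Dose 4 | 113 | 113 | 21 days |
| 120 | 120 − 113 = 7 days after Dose 5 | 141 | 141 | 21 days |
| 148 | 148 − 141 = 7 days after Dose 6 | none stated | 169 | 21 days |

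The matching examinations 7 days after Doses 1 and 2 (Days 8 and 36) keep their own rows. Those after Doses 3 to 5 are folded into the row 28 days after the dose. The visit window in Protocol Table 1 is ±2 days.

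**Selection.**
- Examinations: a legacy record enters if it adds an abnormality, so use depends on the result and the protocol version.
- Vital signs: a legacy record enters if the current visit is empty, so use depends on missingness and version. The value plays no part.
- Laboratory data (SAP 5.3.3.12): the last measurement before each dose is used whatever its value. The SAP therefore already contains a result-neutral rule.

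**Direction.** By default, SAP 5.3 takes percentages over all patients in the arm within the population. The examination rule can add patients to the abnormal count and cannot remove any, so the abnormal rate can only stay the same or rise.

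**Size (illustration).** Let p be the chance that one examination is abnormal and f the share of patients on earlier versions. The documents give neither, nor how long findings persist.

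- If findings persist fully from the legacy visit to the next one, the legacy examination adds nothing and the rate stays at p.
- If the two examinations are independent, a legacy patient's rate is 1 − (1 − p)²:
  - p = 2%: 1 − 0.98² = 3.96%
  - p = 5%: 1 − 0.95² = 9.75%
  - p = 10%: 1 − 0.90² = 19.0%
- The pooled rate under independence is (1 − f)p + f[1 − (1 − p)²]. For p = 5% and the planned 40 patients per arm:

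| f | Pooled rate | Expected abnormal per 40 | Scheduled visit only |
|---|---|---|---|
| 25% | 6.19% | 2.5 | 2.0 |
| 50% | 7.38% | 3.0 | 2.0 |
| 75% | 8.56% | 3.4 | 2.0 |

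On these inputs the rule adds about 0.5 to 1.4 patients per arm per row. Independence is the upper end of the range when findings tend to persist.

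**The case against.** The strongest defence is that little rests on these rows. Physical examination and vital signs are not among the safety endpoints in Protocol 3.4 or SAP 4.3, the tables are descriptive, and keeping every abnormal finding visible is a cautious choice. Allocation is 1:1, so protocol version should balance between arms in expectation. Post-baseline examinations are listed by patient, and Protocol 8.3.5 requires clinically relevant changes to be recorded as adverse events. All of this stands and limits the consequence. It does not justify choosing data by result, because separate rows would keep the same findings visible without distorting the scheduled visits.

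A reader might infer four stronger points that the documents do not support.

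- *Vital signs are also selected by result.* The trigger in SAP 5.3.3.11 is an empty current visit.
- *The vital-sign substitution contradicts the statement* "Only available data will be used, and missing data will not be imputed". Assigning an observed reading to a visit row by a stated mapping is not clearly imputation. What remains is a timing problem.
- *The examination after Dose 6 is lost.* It stays in the by-patient listing and in adverse-event reporting. Day 169 is a complete examination in a separate table, which may explain why Day 148 is unmapped, though the SAP does not say so.
- *Flares suffer the same defect.* SAP 4.3 counts flares "considering ALT values across all measurements taken (scheduled and repeated) during the treatment period". It names no legacy visits, and the current protocol still takes liver panels between Doses 3 to 5 and the next dose.

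**Conclusion.** The point holds for the targeted physical examination. The SAP 5.3.3.9 rule selects by result, applies only to earlier-version patients, and can only raise the abnormal rates at Days 85, 113 and 141 relative to scheduled-visit data. Those rows should not be read against Days 1 to 57.

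The size is unknown. A near-doubling for a legacy patient needs a low abnormality rate and independent examinations 21 days apart; with persistent findings the effect shrinks toward nothing. The effect on the whole row scales with the legacy share. No between-arm bias is expected.

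Two smaller points stand. Abnormal Day 148 targeted examinations have no stated place in a summary table. In the vital-sign table, a reading taken 7 days after a dose can stand in for one due 21 days later, against a ±2-day window, so the affected rows can mix 7-day and 28-day post-dose values. This is a correction to make in descriptive safety reporting; it does not bear on the efficacy conclusions.

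**What to change.** In SAP 5.3.3.9 and Table 14.3.9.1.2, summarise Days 85, 113 and 141 from the examination at that visit only. Show legacy Days 64, 92, 120 and 148 as separate rows with all results, normal and abnormal. Use the number of patients examined at each legacy visit as the denominator, and say so in a footnote, since the SAP 5.3 default is the whole arm. Leave Day 169 in Table 14.3.9.1.1.

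As a secondary change, in SAP 5.3.3.11 and Table 14.3.7.1 either give the legacy vital-sign readings their own rows or footnote, by row and arm, how many readings were substituted.

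The cost is SAP wording, four extra rows with small denominators, and a rerun of one or two descriptive tables. SAP version 2.0 follows the Week 24 analysis, so the rerun may come after unblinded outputs exist. The replacement rule does not depend on results, so this is no obstacle. If a rerun is not practical, footnote the examination rule and the number of legacy examinations merged into each row.
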